8.1.5 Overall summary of analyses to account for missing data

Forest plots will be used to show the primary analysis results along with the missing data sensitivity and alternative estimand analysis results.

It is noted that if the primary analysis is statistically significant, it is not necessarily expected that all sensitivity analyses will also give statistically significant results. If the results of the sensitivity analyses provide reasonably similar estimates of the treatment effect to the primary analysis, this will be interpreted as providing assurance that neither the lost information nor the mechanisms which cause the data to be missing have an important effect on primary analysis conclusions. Based on these outputs and the drug's mechanism of action, the plausibility of the assumptions we make about missing data in the different analyses will be considered and described in the clinical study report.

The methodology described above to explore any potential impact of missing data for the primary endpoint may be repeated for other endpoints if required due to amount or pattern of missing data.

8.2 Analysis plan for immunogenicity data

Serum samples for ADA assessments will be conducted utilizing a tiered approach (screen, confirm, titre) and ADA data will be collected at scheduled visits shown in the CSP. ADA result from each sample will be reported as either positive or negative. If the sample is positive, the ADA titre will be reported as well.

In general, participants with a missing baseline ADA assessment will be assumed to be ADA negative at baseline as a conservative approach to ensure that all participants are included in all analyses. If a positive ADA titre result is reported as ≤ 50 , then the titre will be imputed as 50 for titre summaries. ADA results from samples collected post-dose instead of pre-dose on an IP administration day are considered unreliable and should be excluded from all derivations.

For each participant, the following ADA responses will be evaluated over the entire on-study period through EOT:

- Participants who are ADA positive at any time during the study, including baseline and/or post-baseline (also generally referred to as ADA positive). The proportion of ADA positive participants in a population is known as ADA prevalence.
- Participants who are ADA negative at all assessments, including baseline and postbaseline (also generally referred to as ADA negative).
- Participants who are ADA positive at baseline only.
- Participants who are ADA positive at baseline and at least one post-baseline assessment.
- Treatment-emergent ADA positive (referred to as ADA incidence). A positive postbaseline result and either of the following statements holds:
 - Baseline is ADA negative and at least one post-baseline assessment is ADA positive. This is called treatment-induced ADA positive.
 - Baseline is ADA positive, and the baseline titre is boosted by greater than the variability of the assay (ie ≥ 4 -fold increase) at ≥ 1 post-baseline timepoint. This is called treatment-boosted ADA positive.
- Participants who are persistently ADA positive, which is defined as ADA negative at baseline and having at least 2 post-baseline ADA positive measurements with ≥ 16 weeks between first and last positive, or an ADA positive result at the last available post baseline assessment.
- Participants who are transiently ADA positive, defined as ADA negative at baseline and at least one post- baseline ADA positive measurement and not fulfilling the conditions for persistently positive.
- Participants who are ADA positive with maximum titre $>$ median of maximum titres. The median of maximum titres will be calculated based on the maximum titre of each ADA positive participant within each treatment group (including both baseline and post-baseline measurements).

The responses above will be summarized as counts and percentages by treatment group. The maximum ADA titre over the on-study period will also be summarized for participants in each of the ADA positive response categories listed above. The maximum titre will be derived based on all available ADA titres reported for each participant, including any unscheduled assessments.

ADA response (positive or negative) and titre will be summarized at baseline and at all scheduled post-baseline visits by treatment group. In the event a participant has more than one result within a given visit window, the maximum ADA titre will be used in the by-visit summary. In addition, the ADA response will be presented cumulatively. The cumulative ADA response is positive for a specific visit if a positive ADA result is detected at any time point up to and including the specific visit. If all ADA result are negative up to the specific visit, then the cumulative ADA response is negative for that visit. A summary of the number and percentage of participants who are ADA positive at a post-baseline assessment for the first time by visit will also be presented. A line plot of the proportion of participants who are ADA positive at each visit will be provided.

The proportion of participants with ADA persistently positive response will be summarized by visit and treatment group.

Key participant information will be listed for participants with positive ADA results, including ADA status, titre, benralizumab serum concentration, and eosinophil level.

All analyses will be conducted on the safety analysis set by treatment group unless otherwise specified. All ADA results will be listed.

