1.1.2 Investigational Product Dosing Regimen

Participants who meet entry criteria will be randomized 1:1:2 by the interactive voice/web response system (IxRS) to 1 of the 3 treatment sequences described in Section 1.1.

Blinded IP (benralizumab or placebo) will be administered Q4W at Weeks 0, 4, 8, and 12 (Figure 1).

From Week 16 onwards, participants initially randomized to benralizumab 30 mg will receive benralizumab 30 mg Q4W or Q8W interval, according to their original randomization at Visit 2 (Week 0) (Figure 1).

At Weeks 16, 20, and 24, participants initially randomized to placebo will receive benralizumab 30 mg Q4W. At Week 28, these participants will transition to receive benralizumab 30 mg Q8W interval (Figure 1).

All participants on Q8W regimen from Week 16 onwards will continue to receive treatment containing placebo at their Q4W visit intervals (Figure 1), thus maintaining the blinded treatment regimen.

The final dose of benralizumab or placebo will be administered at Week 48.

Please refer to the clinical study protocol (CSP) for more details.

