3 PRIMARY AND SECONDARY VARIABLES

3.1 General definitions

3.1.1 Baseline definition

Generally, for efficacy data, the last recorded value on or prior to the date of randomization will serve as the baseline measurement. If time is collected, the assessment performed the same day but at a time prior to randomization will be included in the baseline definition. This includes both, the Week 16 primary and the Week 52 final analyses.

Generally, for safety data, the last recorded value on or prior to the date of the first dose of IP will serve as the baseline measurement. If time is collected, the assessment performed the same day but at a time prior to the first dose of IP will be included in the baseline definition. This includes both, the Week 16 primary and the Week 52 final analyses.

For the Peak Pruritus Numeric Rating Scale (NRS), the average of the daily scores for the 7 days prior to the day of randomization will be the baseline. If there is no value prior to the date of randomization, then the baseline value will not be imputed and will be set to missing. Further details on scoring the Peak Pruritus NRS will be provided in Section 3.3.2.

For PROs with recall periods of 1 week or more (POEM, DLQI/CDLQI, HADS, PGI-S, CCI EQ-5D-5L, SF-36v2), the time component of the definition of baseline (ie time of assessment relative to randomization) will not be considered; assessments on the same

day as randomization will be used to calculate baseline. If there is no assessment prior to randomization (or on the same day), then the baseline value will not be imputed and will be set to missing. Further details on scoring for PROs will be provided in Section 3.3.

When time of assessment is not recorded or missing, it is assumed that assessments recorded on the date of first dose of IP were performed prior to dosing, except in cases of protocol specified post-dose assessments. If there is no value prior to randomization (or the first dose of IP, depending on the endpoint), then the baseline value will not be imputed and will be set to missing. No data known to be collected post first dose will be used in determining the baseline value, unless otherwise specified.

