For laboratory results and vital signs, baseline will be defined as the last non-missing assessment prior to first dose of IP. If no time is recorded for an assessment, and the assessment takes place at Visit 2, this will be assumed to be a pre-dose assessment. For physical examinations (complete or brief) baseline data will be collected at Visit 2 before first dose of IP.

Additional analyses for the participants who switch from placebo to benralizumab at Week 16 may be performed where the baseline value is set to the last recorded value prior to starting benralizumab (ie likely the Week 16 measurement) to obtain an assessment of the changes occurring while actually receiving benralizumab.

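### In Week 52 reporting, a placebo-to-benralizumab participant can be classed as treatment-emergent ADA positive from a sample taken before any benralizumab

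*SAP*

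**What the plan says.** **ADA categories.** Appendix 8.2 sets one window for all participants: "the following ADA responses will be evaluated over the entire on-study period through EOT". Treatment-emergent status can be reached in two ways:

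- induced: "Baseline is ADA negative and at least one post-baseline assessment is ADA positive. This is called treatment-induced ADA positive";
- boosted: "Baseline is ADA positive, and the baseline titre is boosted by greater than the variability of the assay", meaning at least a 4-fold rise at one or more later timepoints.

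Neither requires that benralizumab has been given. Persistent positivity needs a negative baseline plus either two or more later positives spanning at least 16 weeks, or a positive last assessment. For a missing baseline, "participants with a missing baseline ADA assessment will be assumed to be ADA negative at baseline".

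**Baseline.** Appendix 8.2 does not define it. Section 3.1.1 gives the general rule for safety data, "the last recorded value on or prior to the date of the first dose of IP will serve as the baseline measurement", and applies it at both Week 16 and Week 52. IP includes placebo: "Blinded IP (benralizumab or placebo) will be administered Q4W at Weeks 0, 4, 8, and 12" (Section 1.1.2). For switchers, Section 3.1.1 permits additional analyses in which the "baseline value is set to the last recorded value prior to starting benralizumab". These are optional and do not mention ADA.

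**Reporting.** Sections 2.1 and 4.1 present Week 52 results by the three randomized sequences, one of which is placebo/benralizumab. Section 4.2.7.10 presents ADA at both Week 16 and Week 52. Sections 8.2.1 to 8.2.4 reuse ADA status for efficacy, safety, eosinophils and PK.

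**The concern.** Treatment-emergent ADA is meant to describe antibody that appears or rises after exposure to the drug. For the placebo sequence the rules start the observation period 16 weeks before that exposure. A transient or non-specific assay positive under placebo then enters the Week 52 incidence of a sequence whose later treatment is benralizumab.

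The label also carries forward. ADA negative in Appendix 8.2 means negative at every assessment, so such a participant joins the treatment-emergent group and also leaves the negative comparator. In Section 8.2.4 the participant's benralizumab concentrations, all measured after the switch, would be grouped by a status that may predate the drug.

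Elsewhere the SAP does restart the clock for switchers: Sections 3.1.5 and 4.1 count rescue use for this sequence at Week 52 from Day 141. Section 2.2.6 also defines a placebo-to-benralizumab extension analysis set. Appendix 8.2 uses neither idea.

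**Working it through.** The SAP states no ADA rate, count or precision, so there is no figure to reproduce. The check applies the written rules to one switcher and then illustrates the size.

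**Step 1: timing**

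| Element | Placebo-to-benralizumab sequence | Source |
|---|---|---|
| First dose of IP, hence baseline | Week 0 (placebo) | 1.1.2, 3.1.1 |
| First benralizumab | Week 16 | 1.1.2 |
| ADA sampling on dosing days | before the dose | 3.3.8 |
| ADA evaluation window | whole on-study period to EOT | 8.2 |

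If ADA were instead treated under the efficacy baseline in Section 3.1.1 (date of randomization), baseline would still precede the placebo period. Either way, any post-baseline sample up to and including a Week 16 pre-dose sample comes before all benralizumab and still counts.

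**Step 2: a participant under the rules**

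- Week 0 negative or missing; one positive at or before the Week 16 pre-dose draw; all later samples negative. "Baseline is ADA negative and at least one post-baseline assessment is ADA positive" is met, so the participant is treatment-induced, hence treatment-emergent, at Week 52. The participant is also transiently positive.
- As above, with a second positive at least 16 weeks after the first. The participant is persistently positive, although the first of the two positives arose under placebo.
- Week 0 positive with a stable titre. The participant is not treatment-emergent. Steady pre-existing reactivity is therefore not caught, unless the Week 0 sample is missing.

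**Step 3: illustration of size**

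Inputs: n = 80 planned in the sequence (Section 1.1.1). Two quantities are assumed, because the SAP does not give them: f, the proportion who turn positive before the switch and meet the rule; and q = 10%, the true treatment-emergent incidence on benralizumab. Independence of the two is also assumed.

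- Expected number labelled before any benralizumab: n × f
- Chance of at least one: 1 − (1 − f)^n
- Week 52 incidence as written: 1 − (1 − q)(1 − f)

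| f | Expected of 80 | Chance of at least one | Incidence as written (q = 10%) |
|---|---|---|---|
| 1% | 0.8 | 0.55 | 1 − 0.90 × 0.99 = 10.9% |
| 2% | 1.6 | 0.80 | 1 − 0.90 × 0.98 = 11.8% |
| 5% | 4.0 | 0.98 | 1 − 0.90 × 0.95 = 14.5% |

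Because some pre-switch positives would become treatment-emergent on benralizumab anyway, the net excess is n × f × (1 − q): 0.72 participants at f = 1% and 3.6 at f = 5%. With the last pre-benralizumab sample as baseline, the incidence would be about 10%. That is approximate, since a participant positive at the new baseline can then count only through a 4-fold rise.

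**The case against.** The strongest reply is that much of the needed information is already planned.

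- Section 4.2.7.10 reports ADA for the 16-week period, where positives under placebo appear under placebo. There they are a legitimate background rate, not an error.
- Appendix 8.2 commits to by-visit response and titre, cumulative response, first post-baseline positives by visit, and full listings. A careful reader can find the pre-switch positives.
- Sections 4.1 and 4.2.8 promise some extension-period tables that summarize time on benralizumab alone for former placebo participants, and Section 3.1.1 allows re-baselining.

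The first two points stand, and they confine the problem to the Week 52 categories and the tables by ADA status. They make the misclassified participants visible but do not correct those categories. The third does not close the gap: the extension tables are not said to include ADA, and the re-baselining is optional.

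A reader might infer that ADA incidence and persistence are overstated across half the trial, or that incidence could double. The documents support neither. The sequence is 80 of 160 planned participants, but only those who meet the conditions in Step 2 are misclassified. Doubling needs outside inputs: for example, 1% to 3% positives per sample over 2 to 4 samples gives 1 − 0.99² = 2.0% up to 1 − 0.97⁴ = 11.5% before the switch. Added to 10% without overlap, the top end looks like 115% inflation; under independence it is 1 − 0.90 × 0.885 = 20.3%, or about 103%. The SAP gives neither the per-sample rate nor, since the visit schedule is in the protocol, the number of samples. The calculation also treats repeat samples in one person as independent.

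**Conclusion.** The point holds as a conditional misclassification in descriptive Week 52 reporting. As written, the rules can label a switcher treatment-emergent, or start the persistence clock, from a sample taken before any benralizumab, and that label enters the summaries in 8.2.1 to 8.2.4. The conclusion rests on reading the general baseline of Section 3.1.1 into Appendix 8.2, which has no baseline of its own, and on ADA being sampled after baseline within the first 16 weeks, which Section 4.2.7.10 implies.

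The direction for treatment-emergent incidence is upward. The size cannot be determined from the SAP; 0.8 to 4 of 80, and 10.9% to 14.5% against an assumed 10%, are illustrations for assumed pre-switch rates of 1% to 5%. ADA is outside the testing hierarchy in Section 4.1.1, so no primary or key secondary conclusion is affected. This is a worthwhile minor correction.

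**What to change.** Add to Appendix 8.2 that, for the placebo-to-benralizumab sequence in Week 52 and extension reporting, ADA baseline is the last sample before the first benralizumab dose and only later samples count as post-baseline. Apply this to the treatment-emergent (induced and boosted), persistent and transient categories, and to the ADA status used in 8.2.1 to 8.2.4.

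Participants in this sequence who never received benralizumab have no such baseline. The set in Section 2.2.6 gives a suitable denominator, with the others shown separately.

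Leave two things unchanged: prevalence (positive at any time in the study), which is meant to span the whole period, and the Week 16 placebo column, which gives the background rate. Re-deriving every ADA category would alter prevalence without need.

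The cost is one derived baseline flag and a footnote explaining that the baseline differs by sequence. No new samples or visits are needed.

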8.2.1 ADA and efficacy

The effects of ADA on the primary and key secondary endpoints calculated through EOT will be evaluated through summary statistics by ADA status (treatment-emergent ADA positive, ADA negative), if enough data are available. However, it could have difficulties to draw solid conclusions due to no comparisons.

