3.2 Primary outcome variable

The proportion of participants with an Investigator Global Assessment (IGA) 0/1 and a decrease in IGA of ≥ 2 points at Week 16 relative to baseline will be used as the primary efficacy variable.

The IGA is an instrument used in clinical studies to rate the severity of AD globally, based on a 5-point scale ranging from 0 (clear) to 4 (severe). The IGA uses clinical characteristics of erythema, infiltration, papulation, oozing, and crusting as guidelines for the overall severity assessment. The validated IGA scale for AD will be completed by the Investigator on an electronic device supplied to the site according to the Schedule of Activities (SoA) (CSP Table 3) to capture these key measures of AD disease activity and describe the overall appearance of AD lesions (Table 4).

Table 4 Investigator Global Assessment Score

Score	Morphological description
0 – Clear	No inflammatory signs of atopic dermatitis (no erythema, no induration/papulation, no lichenification, no oozing/crusting). Post-inflammatory hyperpigmentation and/or hypopigmentation may be present.
1 -- Almost clear	Barely perceptible erythema, barely perceptible induration/papulation, and/or minimal lichenification. No oozing or crusting.
2 -- Mild	Slight but definite erythema (pink), slight but definite induration/papulation, and/or slight but definite lichenification. No oozing or crusting.
3 -- Moderate	Clearly perceptible erythema (dull red), clearly perceptible induration/papulation, and/or clearly perceptible lichenification. Oozing and crusting may be present.

Table 4 Investigator Global Assessment Score

Score	Morphological description
4 -- Severe	Marked erythema (deep or bright red), marked induration/papulation, and/or marked lichenification. Disease is widespread in extent. Oozing or crusting may be present.

A responder at Week 16 is defined as having IGA 0/1 and a decrease in IGA of ≥ 2 points at Week 16 relative to baseline.

In the statistical analyses, a binary variable will take on value 1 if a participant is defined as a responder, and value 0 for non-responder, and will be used as the response variable for the efficacy analysis.

Intercurrent events will be considered as described above in Section Intercurrent Events (Section 3.1.5). Intercurrent events will be considered for analyses and descriptive summaries.

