8.2.2 ADA and safety

Adverse events and SAEs during the study (separately for on-treatment and on-study periods) will be summarized by ADA status (treatment-emergent ADA positive, ADA negative), if enough data are available. The on-treatment and on-study periods are as defined in Section 3.4.1. AEs and SAEs will also be evaluated by causality as assessed by the Investigator. The potential impact of ADA on hypersensitivity will also be assessed if enough data are available.

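### ADA status spans the whole study but is set against Week 16 efficacy and AEs with no time ordering, so the ADA contrast can be diluted or distorted

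*SAP*

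**What the plan says.** SAP Section 8.2 sets one window for the per-participant categories: "For each participant, the following ADA responses will be evaluated over the entire on-study period through EOT". Two of them are used to split outcomes:

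- Treatment-emergent positive, whose main route is "Baseline is ADA negative and at least one post-baseline assessment is ADA positive". The other route is a boosted baseline titre. Neither has a time limit.
- ADA negative: "Participants who are ADA negative at all assessments, including baseline and postbaseline".

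Section 8.2.1 applies this split to efficacy: "The effects of ADA on the primary and key secondary endpoints calculated through EOT will be evaluated through summary statistics by ADA status". Those endpoints have a fixed time point. Section 3.2 states "A responder at Week 16 is defined as having IGA 0/1 and a decrease in IGA of ≥ 2 points at Week 16", and the hierarchy in Section 4.1.1 places the key secondary endpoints at Week 16 too.

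Section 8.2.2 applies it to safety: "Adverse events and SAEs during the study (separately for on-treatment and on-study periods) will be summarized by ADA status".

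Section 8.2 also defines a status that follows time: "The cumulative ADA response is positive for a specific visit if a positive ADA result is detected at any time point", limited to samples no later than that visit. It is used for by-visit presentation; Sections 8.2.1 and 8.2.2 do not call on it.

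**The concern.** A participant who first tests positive at, say, Week 40 has the Week 16 response tabulated as ADA positive, although no antibody had been detected at Week 16. The grouping variable uses information from after the outcome.

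The clearest case is the placebo sequence. Under Section 1.1.2 it first receives benralizumab at Week 16, so any benralizumab-induced antibody must come after its Week 16 response. Splitting that response by whole-study status says nothing about an ADA effect.

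For AEs, events before the first positive sample are counted under ADA positive together with later ones. Participants followed for longer also have more chances both to test positive and to report events.

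Section 4.2.7.10 commits the study to evaluating the association of ADA with safety and efficacy, and these tables are how it does so. At stake is whether they can be read as evidence on that association.

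**Working it through.** **The plan's own figures.** The SAP states no ADA incidence, timing or effect, so there is no ADA figure to reproduce. The 40% response used below is the benralizumab rate assumed in Section 1.2. With 80 per group, 40% against 10% and a two-sided 5% test, the power is 99.5% (pooled normal approximation), which agrees with the stated figure of more than 95%. The ADA point does not depend on it.

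**Room for late positives.** Dosing visits run every 4 weeks from Week 0 to Week 48, which is 13 visits. Four of them (Weeks 0, 4, 8 and 12) precede Week 16, and nine fall at Week 16 or later.

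**Dilution at Week 16.** Let *f* be the share of ever-positive participants first positive after Week 16, and *p* the response in those positive by Week 16. Assume that late positives respond at Week 16 like ADA negatives, at 40%. Then:

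- observed response in ever-positives = *p*(1 − *f*) + 0.40*f*
- observed gap = 0.40 − observed response = (0.40 − *p*)(1 − *f*)

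| *f* | Gap if *p* = 20% (true gap 20 points) | Gap if *p* = 10% (true gap 30 points) |
|---|---|---|
| 0% | 20 | 30 |
| 10% | 18 | 27 |
| 25% | 15 | 22.5 |
| 50% | 10 | 15 |
| 75% | 5 | 7.5 |
| 100% | 0 | 0 |

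Both *p* and *f* are assumptions. In the placebo sequence *f* = 100% for benralizumab-induced antibodies, by design.

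**Bias in the other direction.** Section 3.1.5 counts withdrawn participants as non-responders, and they also give fewer ADA samples. Assume no ADA effect and an overall response of 40%. Let *w* be the share leaving before Week 16, *q* the probability that a stayer is ever positive, and *rq* the same for a leaver. One example, with *w* = 10%, *q* = 20% and *r* = 0.25:

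- response in stayers = 0.40 / 0.90 = 44.4%
- positives: stayers 0.90 × 0.20 = 0.180, leavers 0.10 × 0.05 = 0.005; response = 0.444 × 0.180 / 0.185 = 43.2%
- negatives: stayers 0.90 × 0.80 = 0.720, leavers 0.10 × 0.95 = 0.095; response = 0.444 × 0.720 / 0.815 = 39.3%

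ADA positives look about 4 points better with no true effect. Over *w* = 5% to 20%, *q* = 10% to 30% and *r* = 0.25 to 0.5, the false advantage runs from 1.1 to 9.5 points.

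**AEs.** No arithmetic is needed. Section 8.2.2 uses the on-treatment and on-study periods of Section 3.4.1, and both start at a first dose of IP. An AE in the first weeks is therefore grouped by samples that may be taken many months later.

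**The case against.** **A Week 16 ADA presentation is planned.** Section 4.2.7.10 has ADA shown for the 16-week period as well as for Week 52, and Section 2.1 bases Week 16 analyses on 16-week data. A programmer might therefore cut ADA status at Week 16 at the primary lock. That is a fair reading and narrows the point. But Section 8.2 states no such cut: its only per-participant window is "the following ADA responses will be evaluated over the entire on-study period through EOT". Section 2.1 also allows by-visit summaries of all data in hand at that lock.

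**Section 8.2.1 speaks of endpoints through EOT.** This could mean responses by visit up to the end of treatment, where the status and outcome windows would match better. The phrase is ambiguous, but it does not change the Week 16 definition of the primary and key secondary endpoints.

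**Grouping and exposure adjustment.** Section 8.2 analyses ADA by treatment group, so placebo-sequence participants do not dilute the contrast in the benralizumab groups. Section 4.2.8 reports AEs separately by period, and Section 4.2.8.1 gives key AE tables exposure-adjusted rates. These provisions stand and help with length of follow-up. They do not put the antibody before the event.

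**Low stakes.** The summaries are descriptive, are made only if data suffice, and carry a caution in Section 8.2.1. That is correct, although the caution cites a lack of comparisons, not timing. First-positive counts by visit and full ADA listings let a reader check timing by hand.

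**Stronger readings.** A reader might infer that the plan hides any ADA effect or cannot address the ADA question at all. The documents do not support this. Some contrast remains unless every positive is late, and the direction of bias is not fixed.

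**Conclusion.** The point holds as a defect of time ordering in Sections 8.2.1 and 8.2.2. Followed as written, they group Week 16 responses and AEs by antibodies that may appear only afterwards. The efficacy contrast keeps a fraction (1 − *f*) of its size: 18 to 5 of an assumed 20 points for *f* between 10% and 75%. If positives are mostly early, the loss is small. Under other assumptions a false advantage of about 1 to 9.5 points for ADA positives can arise. Every one of these sizes rests on assumed ADA rates, timing and effect. The only part fixed by the design is the placebo sequence, where benralizumab-induced antibodies cannot precede the Week 16 outcome. The primary analysis, the testing hierarchy and type I error are untouched.

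**What to change.** **Section 8.2.1.** For Week 16 endpoints, classify participants as treatment-emergent ADA positive or ADA negative from samples up to and including Week 16. For later visits, use samples up to that visit. Apply the treatment-emergent definition of Section 8.2: the cumulative response cannot be used unchanged, because it also counts baseline positives whose titre was never boosted. Do not split the placebo sequence's Week 16 outcomes by antibodies arising after Week 16. State what is meant by calculating these endpoints through EOT.

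**Section 8.2.2.** Keep the ever/never table if wanted. Add AE counts and exposure-adjusted rates with both events and person-time split before and after the first positive sample. Moving events without the matching time would create a new bias. Count the placebo/benralizumab sequence from its first benralizumab dose.

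**Cost.** SAP wording, a date of first positive sample and modest programming; no new data. The ADA-positive group at Week 16 will be smaller. Participants who leave before Week 16 will still have fewer samples, so the second bias is reduced but not removed.
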